5.3.2. Alcohol and Tobacco Restrictions

Participants will abstain from alcohol for at least 24 hours prior to each admission to the clinic until each Check-out. Participants may undergo an alcohol breath test or blood/urine alcohol test at the discretion of the investigator.

Use of tobacco or nicotine-containing products (cigarettes [including e-cigarettes], cigars, chewing tobacco, snuff, etc) is prohibited within 28 days prior to signing the informed consent form (ICF) and during the trial. Vaping is not permitted during the trial.

5.3.3. Activity

Participants will abstain from strenuous exercise for 48 hours before each blood collection for clinical laboratory tests. Participants may participate in light recreational activities during the trial (eg, walking, watching television, reading).

5.3.4. Effects on Ability to Drive and Use Machinery

The effect of CVL-354 on the ability to drive and use machines has not been systematically evaluated.

5.4. Screen Failures

Screen failures are defined as participants who consent to participate in the clinical trial but are not subsequently randomized to trial treatment. A minimal set of screen failure information is required to ensure transparent reporting of screen failure participants to meet the Consolidated Standards of Reporting Trials publishing requirements and to respond to queries from regulatory authorities. Minimal information includes demography, screen failure details, and eligibility criteria.

Individuals who do not meet the criteria for participation in this trial (screen failure) at screening may be rescreened once at the discretion of the investigator and after consultation with the sponsor unless screen failure is due to a positive urine drug screen for illicit substances. Rescreened participants will be assigned a new participant number.

6. TRIAL TREATMENTS

Trial treatment is defined as any investigational treatment(s), marketed product(s), placebo, or medical device(s) intended to be administered to a trial participant according to the trial protocol. Investigational medicinal product refers to a pharmaceutical form of any active substance or placebo being tested in this clinical trial and will be used to refer to the trial treatment in this protocol.

6.1. Trial Treatments Administered

A summary of the IMP to be administered during this trial is presented in Table 10.

Table 10: Investigational Medicinal Product Administered

IMP	CVL-354 Solution (Extemporaneous)	CVL-354 Capsules	Placebo	
Туре	Drug	Drug	Drug	
Dose Formulation	Oral solution	Capsule	Matching oral solution vehicle (without active pharmaceutical ingredient) Matching capsule filled with silicified microcrystalline cellulose	
Unit Dose Strength(s)	0.5 mg/10 mL – 500 mg/10 mL	5 mg, 25 mg, 100 mg	Not applicable	
Dosage	Part A Cohort 1	Part A Cohort 3	Not applicable	
Level(s)	0.5, 1.5 mg, 5 mg, or 15 mg	50 mg		
	Part A Cohort 2	Part B Cohorts 2-5		
	45 mg, 90 mg, 150 mg, or 200 mg	25 mg QD, 50 mg QD, 100 mg QD, or 150 mg QD		
	Part B Cohort 1			
	10 mg QD			
Route of Administration	Oral	Oral	Oral	
Sourcing	CVL-354 capsules will be provided by Cerevel. The CVL-354 oral solution preparation will be supplied by Cerevel and the solution will be prepared by the pharmacy of the trial site.			
Packaging and Labeling	Capsule IMP provided by Cerevel will be in 60 cc HDPE bottles and should be stored in accordance with the drug label.			
	The CVL-354 API for oral solution provided by Cerevel and oral solution will be supplied in amber-glass bottles. The bottles will be labeled according to local regulatory requirements and language. Oral solution will be prepared before dosing by the pharmacy of the trial site.			

Abbreviations: API=active pharmaceutical ingredient; HDPE=high-density polyethylene; IMP=investigational medicinal product; QD=once daily.

6.2. Preparation, Handling, Storage, and Accountability

The investigator or designee must confirm appropriate temperature conditions have been maintained during transit (original shipment and/or moving of IMP supply from 1 office or facility to another within the site's network) for all IMP received and any discrepancies are reported and resolved before use of the IMP.

CVL-354 and placebo oral dosing solution will be prepared by site staff and details of the dose preparation requirements will be provided by Cerevel in a separate extemporaneous dispensing record. Prepared doses will be provided in unit dose containers and labeled in accordance with appropriate regulations and the investigator's site labeling requirements.

Only participants enrolled in the trial may receive IMP and only authorized site staff may supply or administer IMP. All IMP must be stored in a secure, environmentally controlled, and monitored (manual or automated) area in accordance with the labeled storage conditions with access limited to the investigator and authorized site staff.

The investigator is responsible for IMP accountability, reconciliation, and record maintenance (ie, receipt, reconciliation, and final disposition records).

Further guidance and information for the preparation, handling, storage, accountability, and disposition of IMP are provided in the pharmacy manual.

6.3. Measures to Minimize Bias: Randomization and Blinding

6.3.1. Participant Assignment to Treatment

Treatment assignments will be based on a computer-generated randomization code provided by the sponsor or designee.

For the food effect evaluation (Part A, Cohort 3), participants will receive the same 50 mg dose and will be randomized to a treatment sequence (fed/fasted or fasted/fed).

Participants who discontinue may be replaced at the discretion of the sponsor and investigator. If a participant is replaced, he or she will receive a mirror randomization number (such that the same sequence [Part A, Cohorts 1 and 2] or treatment [Part B] assigned to the original discontinued participant would be assigned to the replacement participant). Participants who discontinue during Part A (SAD portion) of the trial may be replaced; however, the replacement participant will only need to complete the trial periods that were not completed by the original participant.

Further instructions on replacement participants are available in the Operations Manual.

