4.1.3. Other Design Considerations

Participants will be admitted to the trial site on Day -1 and remain at the clinic through Day 3 of each period (Part A, Cohorts 1 and 2), through Day 3 of Period 2 (Part A, Cohort 3), or through Day 17 (Part B).

Dose-escalation decisions for Part A and Part B will be made by the SRT, comprising sponsor personnel (or designee/supporting personnel) and site investigator or physician designee, as described in Section 4.4.

If a participant discontinues before completing all periods within a cohort or withdraws for reasons unrelated to the safety of the IMP, the participant may be replaced at the investigator's and sponsor's discretion. In Part A, if a participant discontinues from the trial, the replacement participant will complete the rest of original treatment sequence of the discontinued participant.

Trial procedures and their timing are summarized in the Schedules of Assessments for Parts A and B (Section 1.3).

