In the case of an SAE occurring during active treatment, the investigator will contact the medical monitor and notify the sponsor of the event as soon as possible. Dosing will be paused for all participants, until causality is assessed by the investigator and the sponsor. If the SAE is determined (by SRT) to be either drug-related or relationship is unknown, dosing at the current dose level will be stopped, and further dose escalation will be terminated. If the SAE is determined to be not drug-related by the investigator and the sponsor, then the trial may resume at the current dose level.

In addition, the dose escalation will be terminated based on the following PK criteria:

- MAD: If, based on the observed data, the group mean steady state (Day 14) C_{max} or AUC₂₄ (based on total plasma concentrations) of the next planned dose is projected to exceed the maximum exposures in SAD (Part A), that dose will not be explored. Modified doses may be explored if they are not expected to exceed PK stopping criteria.

Progression to the next dose will occur if the last dose was tolerated and after satisfactory review of the available safety, tolerability, and PK data from a minimum of 6 participants (including at least 1 placebo participant) within a treatment period.

The dose increments will be based on observed exposures and forward predictions. The size of the exposure increments may be changed (not exceeding 3.3-fold [half-log] increments) as the trial progresses, dependent upon emerging PK, safety, and tolerability data. Any decision to change the size of the exposure increment will be made jointly by the investigator and the trial team and after careful evaluation of all available data.

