6.3.2. Blinding

During the entire trial, treatment will be blinded such that participants and the investigator and other site personnel (with the exception of pharmacy staff) will not have knowledge of the treatment assignment at any visit.

Treatment assignment will not be blinded for the food effect portion of the trial.

At the initiation of the trial, investigators and site personnel will be instructed on the method for breaking the blind. In case of an emergency, the investigator has the sole responsibility for determining if unblinding of the treatment assignment for an individual participant is warranted. Participant safety must always be the first consideration in making such a determination. If the investigator decides that unblinding is warranted, the investigator should make every effort to contact the sponsor before unblinding a participant's treatment assignment unless this could delay emergency treatment of the participant. The sponsor must be notified within 24 hours after breaking the blind for a trial participant.

Documentation of unblinding should be recorded in the participant's medical record, including the reason for breaking the blind, the date and time the blind was broken, and the names of the personnel involved. Once the blind is broken for a participant, treatment with the IMP may not be reinitiated for that participant.

A list of sponsor personnel who will be unblinded to treatment allocation for the purposes of dose escalation and safety monitoring (SRT) will be provided in a separate document.

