## 1.3. Measures to Minimize Bias: Randomization and Blinding

### 1.3.1. Subject Assignment to Treatment

Treatment assignments will be based on a computer-generated randomization code provided by the sponsor or designee.

For the food effect evaluation (Part A, Cohort 3), participants will receive the same 50 mg dose and will be randomized to a treatment sequence (fed/fasted or fasted/fed).

Participants who discontinue may be replaced at the discretion of the sponsor and investigator. If a participant is replaced, he or she will receive a mirror randomization number (such that the same sequence [Part A, Cohorts 1 and 2] or treatment [Part B] assigned to the original discontinued participant would be assigned to the replacement participant). Participants who discontinue during Part A (SAD portion) of the trial may be replaced; however, the replacement participant will only need to complete the trial periods that were not completed by the original participant.

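### When a code is broken before dosing ends and the participant is replaced, the mirror number lets the investigator know the replacement's treatment

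*Protocol*

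**What the plan says.** **Blinding.** Protocol 6.3.2 states that participants, the investigator and site staff other than pharmacy "will not have knowledge of the treatment assignment at any visit". In an emergency, "the investigator has the sole responsibility for determining if unblinding of the treatment assignment for an individual participant is warranted". The sponsor must be told within 24 hours. The section adds: "Once the blind is broken for a participant, treatment with the IMP may not be reinitiated for that participant". SAP 1.3.2 carries the same text. The food-effect cohort is open-label and is not affected.

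**Replacement.** Protocol 6.3.1 and SAP 1.3.1 share one rule: "Participants who discontinue may be replaced at the discretion of the sponsor and investigator". For anyone replaced, "he or she will receive a mirror randomization number". This number carries the same sequence in Part A Cohorts 1 and 2. For Part B, the "treatment [Part B] assigned to the original discontinued participant would be assigned to the replacement participant". In Part A the replacement does only the periods left uncompleted. Section 6.3.1 refers to an Operations Manual for further instructions.

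**A second wording.** Protocol 4.1.3 and the Synopsis describe replacement of a participant who discontinues before completing all periods within a cohort or "withdraws for reasons unrelated to the safety of the IMP". Section 6.3.1 has no such condition.

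**Escalation minimum.** Protocol 4.4 requires data from a "minimum of 6 participants (including at least 1 placebo participant") before the next dose.

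**The concern.** Each rule is reasonable alone: stopping IMP after a code break is a common convention, and mirror numbers preserve the planned split. Together they carry one participant's disclosed assignment over to another. The emergency provision in 6.3.2 accounts for the investigator's knowledge of the person whose code was broken. It does not account for knowledge of someone who enrols later and whose own code was never opened.

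The stake is the quality of the safety assessment. Treatment-emergent AEs are a primary endpoint. The investigator classifies each AE as related or not related to IMP (Protocol 10.3.3), and the AE-based criteria in Protocol 4.4 depend on drug-related events. For an affected replacement that judgement would be made with the treatment known, and the SAP has no step to identify the participant. The data would be summarised as double-blind.

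**Working it through.** The plan gives no figure to reproduce on this point, so the check is mainly a reading of the sections together, followed by simple counts.

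**Step 1. Does the knowledge carry over in Part B?**
- The investigator breaks the code before the last dose, and IMP may not be restarted (6.3.2).
- The participant discontinues and may be replaced (6.3.1). No exception is made for a disclosed assignment.
- If replaced, the new participant takes the same treatment (6.3.1, SAP 1.3.1).
- The trial has one center (Protocol 4.1) and the investigator shares the replacement decision, so the person who saw the code can link the two participants.

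Allocation is 4:1 in a cohort of 10: 10 × 4/5 = 8 active and 10 × 1/5 = 2 placebo. With no code break, the probability that a participant is on active drug is 8/10 = 0.80. For the mirror replacement of an unblinded participant it is 1 or 0.

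**Step 2. Part A Cohorts 1 and 2.** Each of the four sequences has exactly one placebo period (Protocol Table 8).
- If the code break shows the sequence, every remaining period is known.
- If it shows only the current period and that is placebo, every remaining period is known to be active.
- If it shows only the current period and that is active (Periods 1 to 3), three sequences remain possible. The probability of placebo in the next period is 1/3, against 1/4 beforehand, so knowledge is partial.

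**Step 3. Share of the analysed participants.** The Safety Analysis Set contains all randomized participants with at least one dose (Protocol Table 11, SAP Table 3). A dosed participant who is replaced therefore stays in, and the replacement is added.

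| Part B group | Participants with one replacement | Share of the replacement |
|---|---|---|
| Active, one cohort | 8 + 1 = 9 | 1/9 = 11% |
| Placebo, one cohort | 2 + 1 = 3 | 1/3 = 33% |
| Placebo pooled over five cohorts (SAP 5.1) | 5 × 2 + 1 = 11 | 1/11 = 9% |

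**Step 4. Is replacement needed?** Without it, 9 of the 10 participants in a Part B cohort remain: 7 active and 2 placebo, or 8 active and 1 placebo. Both splits satisfy the minimum of 6 with at least 1 placebo. The PK Analysis Plan (6.3) places the same minimum under a heading covering Parts A and B.

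**The case against.** The case on the other side has real force.

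- **Nothing compels the sequence of events.** Replacement is discretionary, and a sponsor told within 24 hours of a code break can decline it. This makes the event rarer. It does not help once a replacement is agreed, because the only route that 6.3.1 offers is the mirror number.
- **Section 4.1.3 may already exclude many cases.** Emergencies often raise a question about IMP safety, and the condition there can be read to bar replacement for that reason. It is unclear whether it covers both limbs of the sentence or only withdrawal, and 6.3.1 omits it. Even the strict reading leaves emergencies judged unrelated to IMP.
- **The Operations Manual may contain a safeguard.** It may, and it is not among the documents. The blinding commitment, however, is made in the protocol and SAP, and neither has one.
- **The effect on escalation is limited.** The AE criteria in 4.4 count participants on active drug, so a placebo replacement cannot meet them. Severity follows CTCAE where a term is listed, causality of SAEs is also assessed by the sponsor, and the SRT only may consider stopping on those criteria. All of this stands. The investigator's relatedness judgement for other AEs remains exposed.

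A reader might infer that every unblinded participant becomes a discontinued one. The text does not support that: someone unblinded after the last dose loses no IMP and can still complete under Protocol 4.1.4. A reader might also put the share at 1 of 8 active or 1 of 2 placebo. Those figures drop the dosed participant who was replaced, whom the Safety Analysis Set keeps.

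**Conclusion.** The point holds in a limited form. In Part B, a code broken before dosing ends, followed by a replacement, gives the investigator certain knowledge of the replacement's treatment. In Part A Cohorts 1 and 2 that knowledge is full or partial, depending on what the code break shows. The mirror rule then conflicts with the commitment in 6.3.2 for a participant whom the emergency provision does not cover.

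The size is one participant at a time: 1 of 9 active or 1 of 3 placebo in the affected cohort, and about 1 of 11 in the pooled Part B placebo group. These shares assume that the replaced participant had at least one dose, that there is a single such replacement and, for the pooled figure, that five cohorts complete. The knowledge itself assumes that the investigator knows whom the newcomer replaces. The documents give no rate for code breaks, and the event should be rare. It would not undermine the trial's descriptive analyses as a whole, but it is worth closing because the remedy is small.

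**What to change.** Add one sentence to Protocol 6.3.1 and to SAP 1.3.1: a participant whose assignment has been disclosed to the investigator or to other blinded site personnel will not be replaced under a mirror number. The simplest way to apply it is not to replace that participant. Reconcile the replacement conditions in 4.1.3 (and the Synopsis) with 6.3.1, so that one rule states who may be replaced. The provisions on when the code may be broken and on IMP afterwards are not touched.

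The cost is one fewer participant in an affected cohort. If the unblinded participant was on placebo, a Part B cohort is left with 1 placebo participant, which meets the minimum but leaves no room for a second placebo loss. Unmirrored reserve numbers held by the unblinded pharmacy would keep the cohort at 10, but could move the split from 8:2 to 7:3 or 9:1.

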6.3.2. Blinding

During the entire trial, treatment will be blinded such that participants and the investigator and other site personnel (with the exception of pharmacy staff) will not have knowledge of the treatment assignment at any visit.

Treatment assignment will not be blinded for the food effect portion of the trial.

At the initiation of the trial, investigators and site personnel will be instructed on the method for breaking the blind. In case of an emergency, the investigator has the sole responsibility for determining if unblinding of the treatment assignment for an individual participant is warranted. Participant safety must always be the first consideration in making such a determination. If the investigator decides that unblinding is warranted, the investigator should make every effort to contact the sponsor before unblinding a participant's treatment assignment unless this could delay emergency treatment of the participant. The sponsor must be notified within 24 hours after breaking the blind for a trial participant.

Documentation of unblinding should be recorded in the participant's medical record, including the reason for breaking the blind, the date and time the blind was broken, and the names of the personnel involved. Once the blind is broken for a participant, treatment with the IMP may not be reinitiated for that participant.

A list of sponsor personnel who will be unblinded to treatment allocation for the purposes of dose escalation and safety monitoring (SRT) will be provided in a separate document.

6.4. Trial Treatment Compliance

The time and dose of each IMP administration, along with information on any missed or inappropriately administered dose, will be recorded in source documents and the eCRF. Compliance will be ensured by a hand and mouth check during the oral dosing administration.

6.5. Prior and Concomitant Therapy

All prescription and over-the-counter medications are prohibited from 28 days prior to first dose of IMP through the end of the trial (as defined Section 4.5) with the exception of acetaminophen (maximum total daily dose of 1 g) and topical steroid use as needed for treatment of an AE. Use of herbal medications, vitamins, and supplements is also prohibited during the trial.

The investigator will record all medications and therapies taken by the participant for treatment of an AE until the end of the trial. The following information will be recorded in the eCRF: medication, indication, dose, frequency, route, start date, and end date.

The medical monitor should be contacted if there are any questions regarding concomitant or prior therapy.

6.6. Dose Modification

Guidance for dose escalation/stopping rules is provided in Section 4.4.

The decision to proceed to the next dose level of CVL-354 in successive cohorts/periods will be made by the SRT based on a full review of the safety, tolerability, and preliminary PK data obtained from the completed prior doses.

If ongoing data surveillance during the treatment interval reveals consistent notable AEs or safety concerns at a dose, which are determined to be attributable to the drug treatment, continued dosing within the cohort will be temporarily halted and no participants will be dosed until full safety review can take place to determine if dose modification or termination of the cohort are appropriate.

6.7. Intervention after the End of the Trial

There will be no provision of CVL-354 for participants after they complete or discontinue treatment in this trial.

7. DISCONTINUATION OF TRIAL TREATMENT AND PARTICIPANT DISCONTINUATION/WITHDRAWAL

7.1. Discontinuation of Trial Treatment

After treatment assignment, a participant may stop treatment permanently for a variety of reasons. Treatment discontinuations may be initiated by a participant or may become medically necessary due to AEs, required treatment with a disallowed medication or therapy, or other issues, as determined by the investigator. If IMP is permanently discontinued, the participant will be encouraged to remain in the trial for the evaluations at safety follow-up. See the Schedule of Assessments (Section 1.3) for data to be collected at the time of discontinuation of IMP and follow-up and for any further evaluations that need to be completed.

The IMP may be discontinued for any of the following reasons listed below:

- Adverse event
- Protocol deviation
- Noncompliance with study schedule
- Withdrawal by participant
- Physician decision

If a participant discontinues the IMP due to an AE, the investigator or other trial personnel will make every effort to follow the event until it has resolved or stabilized.

